### 2. The Asthma Medication Ratio (AMR)

This is a metric used by HEDIS to assess quality of asthma care in healthsystems. It is calculated as the rate of controller therapy refills over the controller therapy plus the rescue therapy refills over a period of one year. In a subset of enrolled patients, we will use the available pharmacy reported fill data from the patient's health care system plus the ICS fill data from Teva for the intervention group to calculate AMR in the enhanced usual care and intervention arms.

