The analyses on the exploratory outcomes will also be performed. The rate on asthma deteriorations will be reported by treatment groups. The composite endpoint of asthma deteriorations or exacerbations will be analyzed using the same Andersen-Gill version of the Cox proportional hazards model as used in the primary analysis. The Asthma APGAR data will be analyzed using the same mixed model approach as described above in the Asthma Control Test (ACT) score analyses.

Data on the Asthma Medication Ratio (AMR) during the follow-up months, the total health care utilization (i.e., total number of visits made to the enrolling sites, total number of ED visits, and total number of hospitalizations), and asthma related health care utilization (i.e., number of visits made to the enrolling sites, number of ED visits, and number of hospitalizations for which asthma is a first or second diagnosis) will be summarized. Differences between two randomized treatment groups on these variables will be compared using either t-test or Kruskal-Wallis test if full follow-up is available on everyone or Poisson or Negative Binomial regression models with time as an offset to account for differential duration of follow-up.

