## **8. Sample Size and Power Considerations**

Sample size and power calculations were performed using PASS software (Hintze 2011), using the similarity of inference between the Andersen-Gill models and Poisson regression.

For the primary efficacy outcome, power calculations were based on an estimated primary event intensity of 0.4 per year (0.5 per 15 months) in the control arm (as seen in the BELT study), 15 months of follow-up for each individuals with an annualized rate of uniform loss to follow-up of 25% (31.25% in 15 months of follow-up) and a two-sided significance level of 0.05. With these assumptions, 1200 up to patients (600 per arm) yields 80% power to declare a reduction of 23.5% in the intensity of exacerbations as statistically significant. Even if the event rate were lower at .35 we would still have 80% power to detect a 25% difference. This difference is clinically meaningful and is well within the 25-50% (and more likely 40-50%) (O'Byrne 2006, Rabe 2006, Buhl 2012, Papi 2013, Calhoun 2012) reductions noted with such studies.

For subgroup analysis, using these same assumptions, with group size of 600 (300/arm), at a power level of 80% we would be able to detect an expected change of 32%, still well within the noted effects.

Power for secondary outcome comparisons were also calculated. Based on results observed in the BELT study, we expect the standard deviations in ASUI scores to be 0.23 in each arm. Thus, we will have 80% power to detect a difference of 0.04 in ASUI scores between treatment arms. Assuming standard deviations of 4.9 in each treatment arm on the ACT questions score, we will have 80% power to detect a difference of 0.96 in ACT scores.

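### The Asthma Medication Ratio, a share between 0 and 1, shares a rule with the utilization counts that would send it to a count model with a time offset

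*Combined protocol and SAP*

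**What the plan says.** Section III.D.2 defines the AMR as "the rate of controller therapy refills over the controller therapy plus the rescue therapy refills over a period of one year". It limits the measure to patients with fill data: "In a subset of enrolled patients, we will use the available pharmacy reported fill data".

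Section III.E.7 opens its list of variables with "Data on the Asthma Medication Ratio (AMR) during the follow-up months, the total health care utilization" and then adds asthma-related utilization. One rule covers the whole list: "Differences between two randomized treatment groups on these variables will be compared using either t-test or Kruskal-Wallis test if full follow-up is available on everyone". When that condition fails, the rule prescribes "Poisson or Negative Binomial regression models with time as an offset to account for differential duration of follow-up". The AMR is not carved out, and no other section gives it a method of its own.

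Three other places bear on which branch applies:

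- Section II.C.7 (Follow-up Intensity) plans up to 15 months of questionnaires, but 14, 13 and 12 months for patients enrolled in February, March and April 2020.
- Section III.E.8 assumes "an annualized rate of uniform loss to follow-up of 25" per cent, which is 31.25% over 15 months.
- Section III.E.1 has a t-test or Kruskal-Wallis default for continuous variables, but it gives way wherever another section specifies a method.

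**The concern.** The rule suits visits, ED visits and hospitalizations, which accumulate with time at risk. The AMR does not: its numerator and denominator are counted over the same window, so time cancels. If time enters again as an offset, the model treats an AMR of 0.5 over 6 months as 2.5 times an AMR of 0.5 over 15 months. A count model also ties the variance to the mean, which is too large for a quantity bounded by 0 and 1.

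At stake is whether a real AMR difference between the arms would be seen, and whether different retention in the arms could look like one. The AMR is described as a health-system quality metric, and Section II.E.1 records that policy stakeholders asked about total asthma medication use. The result would therefore be read outside the trial team.

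**Working it through.** **Inputs from the documents.** AMR definition (III.D.2); the two-branch rule (III.E.7); follow-up of 12 to 15 months (II.C.7); 31.25% uniform loss over 15 months and two-sided 0.05 (III.E.8); 1:1 allocation (II.C.3).

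**Assumed, because the documents do not give them.** AMR means of 0.50 and 0.57, SD 0.15 to 0.40, 100 to 300 patients per arm with fill data, and the III.E.8 loss carried over to this subset.

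**1. The plan's own figure.** The plan states no figure for the AMR. The power figure that carries the loss assumption reproduces:

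- Mean exposure = 1.25 × (1 − 0.3125/2) = 1.055 years.
- Events = 600 × 0.4 × 1.055 = 253.1 and 253.1 × 0.765 = 193.6.
- SE of the log rate ratio = sqrt(1/253.1 + 1/193.6) = 0.0955.
- Power = Φ(0.268/0.0955 − 1.96) = 80.1%, against 80% stated.

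**2. The quantity estimated.** With a log(time) offset, the arm-level estimate is total AMR divided by total time. In simulation, a true AMR of 0.50 comes out as 0.41 per year with complete 12 to 15 month follow-up and 0.48 with the assumed loss. When AMR was built from simulated refill counts, its correlation with follow-up time was about 0, so there is nothing for the offset to adjust.

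**3. Between-arm ratio.** Under uniform loss, mean exposure is proportional to 1 − loss/2. With no true AMR difference, the fitted ratio is the inverse ratio of exposures:

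- Equal loss: 1.00.
- 31.25% vs 41.25%: 0.84375/0.79375 = 1.06.
- 25% vs 40%: 0.875/0.80 = 1.09.
- 20% vs 45%: 0.90/0.775 = 1.16.

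**4. Width of the intervals.** At equal exposure, model-based Poisson SE / true SE = sqrt(mean)/SD. A 0-1 variable has variance of at most mean × (1 − mean), so this factor is at least 1/sqrt(1 − mean), or 1.41 at a mean of 0.5, whatever the SD. At SD 0.25 it is 0.707/0.25 = 2.83. Loss makes exposure vary, which adds real sampling variation and lowers the factor. Simulation with loss, means 0.50 vs 0.57:

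| Per arm | SD | SE too wide by | Power, model-based SE | Power, robust SE | Power, direct comparison |
|---|---|---|---|---|---|
| 200 | 0.15 | 3.1 | 0.1% | 84% | 99.6% |
| 200 | 0.25 | 2.4 | 0.3% | 61% | 80% |
| 200 | 0.30 | 2.1 | 1.3% | 51% | 64% |
| 200 | 0.40 | 1.6 | 4.9% | 36% | 41% |
| 100 | 0.25 | 2.3 | 0.1% | 35% | 49% |
| 300 | 0.25 | 2.4 | 2.7% | 80% | 93% |

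**5. Negative binomial.** It can only add variance to the Poisson. With AMR built from simulated refills (200 per arm, no difference), the fitted dispersion went to about zero. The SE was 0.144, the same as Poisson, against a sampling SD of about 0.062.

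**6. Robust standard errors.** At 200 per arm and SD 0.25 the robust SE is 0.058 against a true sampling SD of 0.057, so the width is right. The estimate is still AMR per year and the bias in step 3 remains. Part of the power is also lost (61% vs 80%), because follow-up time enters as noise.

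**The case against.** **The count branch may not be reached.** The 25% loss is stated for the primary outcome, which is captured by questionnaire; the AMR comes from pharmacy fills. Section III.E.10 says refill and claims data can still be reached unless consent is withdrawn. Section III.D.2 uses a one-year window, and every patient is planned for at least 12 months. Section III.E.10 also provides multiple imputation for other analyses. What stands is that loss in the AMR subset could be well below 31.25%. But the condition requires full follow-up on everyone, so one withdrawal defeats it. Section III.E.7 refers to the follow-up months, not to a one-year window. Nothing says that the condition is judged after imputation.

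**The sentence may be loose drafting.** The offset's stated purpose makes sense only for quantities that accrue, and the Section III.E.1 default is already a t-test or Kruskal-Wallis test. A sensible analyst might apply that to the AMR. That is a fair account of what may have been meant, but the written rule names the AMR first and overrides the default.

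**Stronger readings a reader might infer.**

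- *That the AMR comparison has almost no power.* This needs model-based standard errors and assumed inputs. Section III.E.7 does not name a variance estimator; robust errors are specified only for the primary model.
- *That false AMR differences would be declared.* The bias needs unequal follow-up by arm, which the documents do not predict. With model-based errors it would rarely reach significance: 1.7% of simulated trials even at 20% vs 45% loss. With robust errors that protection goes: 31% at 25% vs 40% loss.
- *That the utilization count models are also wrong.* Nothing here shows that. A time offset is appropriate for those counts.

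**Conclusion.** The concern holds as a wrong rule for one exploratory outcome. Three parts need no assumed AMR mean, SD or subset size once the count branch is used: the model estimates AMR per year; the between-arm ratio depends on equal follow-up; and, at equal exposure, model-based intervals are too wide by at least 1/sqrt(1 − mean), which negative binomial cannot repair.

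The sizes do rest on assumptions. The 1.6 to 3.1 range depends on SDs of 0.40 to 0.15 and the assumed loss. The 61% vs 80% power comparison depends on 200 per arm, SD 0.25 and means of 0.50 and 0.57. The ratio of 1.06 depends on a 10-point gap in loss. With equal follow-up the ratio is right on average, and with model-based errors the fault is conservative. The AMR is measured in a subset of unstated size and supports no primary or secondary conclusion, so the point is worth correcting but does not threaten the trial's main result.

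**What to change.** Take the AMR out of the shared sentence in Section III.E.7 and give it its own method with no time offset. Two options:

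- a t-test or Kruskal-Wallis test on the AMR, matching the Section III.E.1 default for continuous variables; or
- a fractional-logit or binomial model of controller fills out of all fills, with robust standard errors.

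Keep the Poisson or negative binomial offset models for the utilization counts only. The same edit could state the AMR observation window (III.D.2 and III.E.7 describe it differently) and the handling of patients with no fills, for whom the ratio is undefined.

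The cost is about two sentences in the analysis plan. No new data are needed and no other analysis changes.

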## **8. Sample Size and Power Considerations**

Sample size and power calculations were performed using PASS software (Hintze 2011), using the similarity of inference between the Andersen-Gill models and Poisson regression.

For the primary efficacy outcome, power calculations were based on an estimated primary event intensity of 0.4 per year (0.5 per 15 months) in the control arm (as seen in the BELT study), 15 months of follow-up for each individuals with an annualized rate of uniform loss to follow-up of 25% (31.25% in 15 months of follow-up) and a two-sided significance level of 0.05. With these assumptions, 1200 up to patients (600 per arm) yields 80% power to declare a reduction of 23.5% in the intensity of exacerbations as statistically significant. Even if the event rate were lower at .35 we would still have 80% power to detect a 25% difference. This difference is clinically meaningful and is well within the 25-50% (and more likely 40-50%) (O'Byrne 2006, Rabe 2006, Buhl 2012, Papi 2013, Calhoun 2012) reductions noted with such studies.

For subgroup analysis, using these same assumptions, with group size of 600 (300/arm), at a power level of 80% we would be able to detect an expected change of 32%, still well within the noted effects.

Power for secondary outcome comparisons were also calculated. Based on results observed in the BELT study, we expect the standard deviations in ASUI scores to be 0.23 in each arm. Thus, we will have 80% power to detect a difference of 0.04 in ASUI scores between treatment arms. Assuming standard deviations of 4.9 in each treatment arm on the ACT questions score, we will have 80% power to detect a difference of 0.96 in ACT scores.

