## **2. Asthma in African Americans and Hispanics and Latinos**

Asthma has a broad impact on African American (AA) and Hispanic and Latino (H/L) populations stemming from disparities in disease-specific and healthcare-specific factors. These groups bear a disproportionate share of asthma morbidity and mortality (Gold 2005). Asthma is more prevalent in these populations (35% and 100% higher in AA and H/L, respectively than in Caucasians) (Akinbami 2011, Moorman 2011, Rose 2006, Smith 2005). There are also disparities in morbidity independent of prevalence. Both AAs and H/Ls have double the rates of asthma related ED (emergency department) visits and hospitalizations as Caucasians (Crocker 2009, Ginde 2008, Law 2011, Ash 2006, Boudreaux 2003, Gupta 2006), and 50% higher rates of re-hospitalization (Ash 2006). African Americans experience two to three times the death rate due to asthma as Caucasians. Among Puerto Rican H/Ls, rates of asthma exacerbations are 30% higher (Moorman 2013) and asthma-related death rates are 75% to 200% higher (Homa 2000). *Our team recently completed a study comparing two long-acting bronchodilator asthma medications in >1,000 African Americans across the country (BELT study submitted for publication). One-third of the subjects had an exacerbation requiring corticosteroids in a year.*

Health care and use of asthma medications differs in AA and H/L populations compared with whites as well. AAs are less likely than non-Hispanic whites to receive asthma care that follows guidelines (e.g., use of inhaled corticosteroids), and to be educated on self- management strategies (Krishnan 2001). H/Ls with current asthma have a 60% higher likelihood of having a health service deficit (a composite variable defined as health insurance status, having a healthcare provider and a routine physical exam, and deferring medical care due to cost) (Lutfiyya 2011). They also are found to have decreased access to asthma specialists (Clement 2008) and to insufficiently use anti- inflammatory medications (Hunninghake 2006). Both AAs and H/Ls are less likely than whites to receive adequate and timely follow up after ED treatment for asthma (64% and 41% less likely, respectively) (Shields 2004). Of greatest concern, although the morbidity seems to be decreasing among whites, it is not changing among minorities. Asthma ED visits decreased by 25% in whites ( $p=0.02$ ) from 1993 to 2005 but did

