## **7. Evidence supporting the PARTICS strategy**

Systematic reviews of efficacy studies suggest that a PARTICS approach can reduce exacerbations by 25 to 50% (Cates 2013, Kew 2013) and more likely 40-50% in adults (O’Byrne 2006, Rabe 2006, Buhl 2012, Papi 2013, Calhoun 2012). One major gap in

knowledge is whether such results are achievable in a real-world setting with high-risk populations. Previous studies were explanatory studies with restricted patient entry. It is estimated that only 5% of asthmatics can enter such trials (Herland 2005, Travers 2007). The trials contained few if any AA or H/L. Further, some of these studies involved long- acting beta-agonist withdrawal during the run in, and thus may have made the study populations more likely to respond to PARTICS (Cates 2013). Another knowledge gap is whether this reliever-triggered approach can be implemented in health care systems that treat substantial numbers of minority patients. Review articles and a recent editorial have called for this strategy to be tested in different asthma populations and varied real-world settings ([name] 2014, Papi 2009). We have strong data from efficacy studies to suggest that a PARTICS approach will be successful. As mentioned in **section I.B.5** above, 'barriers to adherence to controller asthma therapy', a major implementation barrier to asthma pharmacotherapy involves issues of patient acceptance and patient activation. Current national guidelines recommend daily ICS therapy for asthma control. However, patients fill less than a quarter of their ICS prescriptions and asthma morbidity remains high (Apter 2011, Williams 2010). Dr.

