Efficacy trials generally include only 5% of eligible asthmatics (Herland 2005, Travers 2007). In contrast, we have set broad eligibility criteria including allowing patients with a COPD diagnosis who meet the following criteria with regard to the COPD diagnosis: patient is a never smoker without any other lung disease or any other disease that might cause airway obstruction such as: Cystic Fibrosis, Connective Tissue Disease, premature birth, organ transplantation, bronchiectasis, sarcoid, and obliterative bronchiolitis; a former smoker with normal PFTs done after the person quit smoking; a current smoker with normal PFTs done in the past 24 months; a current or former smoker with obstruction on PFTs with normal diffusing capacity in the past 24 months and demonstrated reversibility of 12% or more at any time. This study includes smokers and COPD is a common co-diagnosis in patients from communities where smoking is prevalent. This approach is much more pragmatic and inclusive of patients who are likely to benefit from the intervention.

Furthermore, from our BELT study, we know that if we enroll patients on ICS who are not well

controlled using a standard asthma control instrument, or who are on an ICS/LABA, that one third will experience exacerbations over the next year. Additionally, patients with a history of exacerbation are at high risk for others (Miller 2007). In contrast to prior efficacy studies, we are not excluding current smokers (up to 25% of asthmatics), past smokers (10%- 25% of asthmatics and an even higher proportion of those turned away in our prior studies), or those with other comorbidities, or those who use other medications. We exclude only patients who cannot provide consent or who are not able to physically participate. We have included provisions for low literacy by providing oral materials for consent and a voice response system option in English and Spanish for those with limited literacy.

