### **4. Statistical Analysis for Primary Outcome**

The primary aim of the study is to determine the impact of PARTICS on asthma outcomes in a minority population consisting of African American and Hispanic/Latino adults. The primary outcome of this study will be the intensity of asthma exacerbations during the months of follow-up between those patients randomized to addition of PARTICS to provider-educated care vs. those who continue with provider-educated care alone.

Rate of asthma exacerbations per year will be reported for two treatment groups. Annualized rates of count outcomes will be summarized using the annualized mean occurrence based on the Poisson model.

Exacerbations rates during follow-up will be compared using the Andersen-Gill adaptation of time-to-event Cox proportional hazards model with robust standard errors to account for potential multiple occurrences of the outcome in each patient (Andersen Gill, 1982). This model was selected over the more commonly used time to first event Cox model for two reasons. First, we believe that total experience during follow-up matters more to patients than the onset of the first exacerbation. Second, the power is increased when multiple events can be included. The covariates in the primary comparison will include: study center (to account for any geographic variation in patterns of care), h/o exacerbations in the past year (y/n), on ICS/LABA prior to randomization (Y/N), race/ethnicity, smoking status (as defined for subgroups), age, BMI (body mass index), and gender since all may influence the rate of exacerbations or the response to corticosteroids. The primary effect will be based on the randomized treatment arm indicator

variable.

Time from randomization to first asthma exacerbation will be compared using the log-rank test. In addition, survival curves will be constructed for this time-to-event endpoint using Kaplan-Meier method.

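### Does the 80% power claim fail because the exacerbation calculation assumes Poisson variance and the detectable effect sits at the edge of the expected range?

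*Combined protocol and SAP*

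**What the plan says.** Section III.E.8 sizes the trial "using the similarity of inference between the Andersen-Gill models and Poisson regression". Its inputs are a control rate of 0.4 exacerbations per year, 15 months of follow-up, uniform loss of 25% per year (31.25% over 15 months), two-sided alpha 0.05 and 600 patients per arm. It states that this "yields 80% power to declare a reduction of 23.5% in the intensity of exacerbations as statistically significant". It adds two further 80% power claims: a 25% reduction if the control rate is 0.35, and 32% for a subgroup with 300 per arm. It then comments: "This difference is clinically meaningful and is well within the 25-50% (and more likely 40-50" percent).

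Section III.E.4 analyses the primary outcome with an Andersen-Gill Cox model "with robust standard errors to account for potential multiple occurrences of the outcome in each patient". The model adjusts for eight covariates, among them exacerbation history, "since all may influence the rate of exacerbations or the response to corticosteroids".

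Section II.C.1 notes that "patients with a history of exacerbation are at high risk for others". Section I.B.2 says of the earlier trial in African American adults: "One-third of the subjects had an exacerbation requiring corticosteroids in a year".

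Section I.B.7 gives two effect ranges. The first says that the strategy "can reduce exacerbations by 25 to 50" percent. The second is 17% to 47%, cites the same two systematic reviews, and is tied to comparison with regular LABA-ICS treatment.

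**The concern.** Two things catch the eye.

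First, the power formula uses Poisson variance while the planned test uses a robust variance, which widens when patients differ in underlying risk. The protocol expects such differences, since it names prior exacerbation as a strong risk factor and adjusts for seven other factors. Section III.E.7 even allows a negative binomial model for utilization counts. Yet section III.E.8 varies only the event rate, never the dispersion. The planned numbers also leave no slack, because the calculation needs 598.2 of the 600 patients per arm. Any heterogeneity left after adjustment would put power below 80%.

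Second, 23.5% is below a range of 25-50% and 25% is its boundary, so neither is comfortably inside it. The other range in section I.B.7 extends down to 17%, where power is much lower. A reader could come away with too favourable a view of the trial's chance of success.

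**Working it through.** **Inputs (section III.E.8).** Control rate 0.4 per year; 1.25 years planned; 31.25% lost uniformly; n = 600 per arm; z = 1.96.

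Mean follow-up: 1.25 × (1 − 0.3125/2) = 1.0547 years.

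**The plan's own figures.** Power = Φ(|ln RR| / √(1/E0 + 1/E1) − 1.96), where E0 and E1 are the expected events in the control and intervention arms.

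- *Main case, RR 0.765.* E0 = 600 × 0.4 × 1.0547 = 253.1; E1 = 193.6. The standard error is √(0.003951 + 0.005164) = 0.0955. Then 0.2679/0.0955 − 1.96 = 0.846, so power is 80.1%.
- *Rate 0.35, RR 0.75.* E0 = 221.5; E1 = 166.1; standard error 0.1026; power 80.0%.
- *Subgroup, 300 per arm, RR 0.68.* E0 = 126.6; E1 = 86.1; standard error 0.1397; power 78.8%. The Schoenfeld formula gives 80.3%.

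All three agree with the document to within the choice of formula.

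**Sensitivity to dispersion (k is an assumption; the documents give none).** Let each patient's rate be multiplied by a gamma variable with mean 1 and variance k. With uniform loss, E[t²] = 0.6875 × 1.25² + 0.3125 × 1.25²/3 = 1.2370, and

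Var(log RR) = 1/E0 + 1/E1 + 2k·E[t²] / (600·E[t]²).

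| k | Power at 23.5% | Reduction detectable with 80% power | Patients with ≥1 event in a year at 0.4/yr |
|---|---|---|---|
| 0 | 80.1% | 23.5% | 33.0% |
| 0.25 | 76.2% | 24.6% | 31.7% |
| 0.5 | 72.5% | 25.6% | 30.6% |
| 1 | 65.8% | 27.4% | 28.6% |

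The last column is 1 − e^(−0.4) for k = 0 and 1 − (1 + 0.4k)^(−1/k) otherwise. Simulation of 4,000 trials with robust variance and no covariates gave power of 80.5%, 76.7%, 73.5% and 66.1% for the four rows.

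**What the prior-trial summaries allow.** A rate of 0.4 per year with one-third affected matches k = 0. If one-third is held fixed, the mean rate must be ((2/3)^(−k) − 1)/k, which is 0.427, 0.449 and 0.500 for k = 0.25, 0.5 and 1. Power at 23.5% is then 78.6%, 76.5% and 72.4%. A rate of 0.50 does not round to 0.4, so k = 1 fits the stated summaries poorly.

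**Validity of the test.** In a second simulation with no treatment effect, the robust test rejected in 5.1% and 4.6% of trials at k = 0.5 and 1. A test using Poisson variance rejected in 7.4% and 9.8%. The planned robust variance is therefore the right protection.

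**Power across the quoted effects (Poisson variance, 0.4 per year).** 17%: 51%. 23.5%: 80%. 25%: 85%. 40%: above 99%, and still 99% at k = 1.

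**The case for a change.** The best argument for a change is that it would be cheap. Section III.E.9 already plans blinded monitoring of the event rate to judge whether power is sufficient. For counts with extra variation the rate alone cannot answer that, whereas the pooled variance could, from the same data and without unblinding. The check against the one-third figure is also rough: both summaries are rounded, section II's description of the patient population says more than one-third, and section IV.C says patients in that trial were followed for up to 18 months. Moderate heterogeneity is therefore not excluded. Covariate adjustment removes only the part that the listed factors explain.

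All of this stands as far as it goes: a dispersion sensitivity would be informative, and its absence is a gap in detail. But no action hangs on it. The concern itself seeks neither more patients nor a different test. Section II.C.7 dates the end of enrolment to 30 April 2020, so a revised planning figure could not change the trial's size. The loss assumption may also be pessimistic, because section III.E.10 plans to keep collecting the primary outcome from records. With no loss at all, power at 23.5% would be 86%, 83%, 79% and 72% for k = 0, 0.25, 0.5 and 1.

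On the effect range, the criticism of the wording is correct. The two ranges need not contradict each other, since the lower one is limited to one comparator and the reference titles of the two reviews name different comparators. The text does not settle this. Section III.E.8 does not claim to power the trial for a 17% effect.

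**Conclusion.** No change to the plan follows. The exacerbation power figures are calculated correctly, and their Poisson basis is named. The ASUI and ACT figures rest on standard deviations and are not touched. Residual heterogeneity would lower power at 23.5% to about 76%, 73% or 66% for k = 0.25, 0.5 or 1. Those values of k are assumptions, and the prior-trial summaries are compatible with little dispersion. If it is present, the robust standard errors in section III.E.4 keep the test valid, so the cost is power alone.

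The statement that the detectable effect lies comfortably inside 25-50% is inaccurate, and section I.B.7 leaves its two ranges unexplained. Both are slips in the justification and alter no analysis or conclusion. A detectable effect at or just below the bottom of the expected range is to the design's credit: under Poisson variance at 0.4 per year, power is at least 85% for any true reduction of 25% or more.
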